6.3.1.1 Evaluation of NK cell function

NK cell function will be measured by flow-based assay as described in our previous study.⁸⁹ Briefly, K562 and Raji cells are exposed to varying ratios of CD56+ NK cells enriched from the patient's peripheral blood. In each assay, the total number of target cells is held constant and 3-fold serial dilutions of the effector cells, performed in triplicate, are established. The percent lysis is measured on the target cells directly as a percentage of 7AAD+ cells. Background (minimum) 7AAD uptake is calculated from targets incubated without effectors. The percent lysis (NK cell lytic activity) is simply calculated as: (% sample 7AAD uptake - %minimum 7AAD uptake).

The NK functional response 1 day and 1 month post NK cell-enriched DLI is defined as percent increase of NK cell lytic activity at 1 day and 1 month post NK cell-enriched DLI compared with NK cell lytic activity pre NK cell-enriched DLI.

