6.3 Secondary Objectives

1. To evaluate the recovery of immune cell populations pre and post infusion in patients receiving NK cell-enriched DLI administered alone or administered with TLR9 ligand, DUK-CPG-001.
2. To evaluate the immune function with antigen specific recovery with Elispot, Immunoscope, and flow-cytometric cytokine assay, and functional NK lysis assay, pre and post infusion in patients receiving NK cell-enriched DLI administered alone or administered with TLR9 ligand, DUK-CPG-001.

The repeated measurements of immune cell numbers and immune function will be plotted against time for each patient. The means of the measurements across patients will be calculated with their 95% confidence intervals. These means will also be plotted against time to show the change with time. The generalized estimating equation method will be used to estimate the rates of change of the mean cell numbers and mean immune function over time, along with their 95% confidence intervals.

6.31 Secondary objectives 1 and 2:

Evaluation of the recovery of immune cell populations pre and post infusion will be performed.

Immunophenotype

NK cell: CD3-CD56^{bright}CD16-, CD3-CD56^{bright}CD16+, CD3-CD56^{dim}CD16+

CD3+ T cell: CD3+

CD4+ T cell: CD3+CD4+

CD8+ T cell: CD3+CD8+

$\gamma\delta$ T cells: CD3+ $\gamma\delta$ TCR+

B cell: CD19+, CD3-, CD16-, CD56-

Regulatory T cell: CD4+, CD25+, CD62L+

Cytotoxic T cell: CD8+, CD57+, CD28-

Activated T cell: CD8+, HLA-DR+

Recent thymic emigrants: CD4+, CD45RA+/CD45RO-, CD62L+

Plasmacytoid dendritic cell: CD123+, CD11c-

Myeloid dendritic cell: CD123-, CD11c+

NKT cell: CD3+, CD16+/CD56+

Quantification of these lymphoid subsets were performed by flow cytometry on fresh peripheral blood prior to, and then at 1 day, and 1 month after each NK cell enriched DLI and at 3, 6, and 12 months following the last NK enriched DLI.^{87,88} The median number of these cell populations will be tabulated at each time points. A plot of number of these against time point will be drawn, using a separate line for each patient.

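### The NK functional response is a percent increase over a background-subtracted baseline that can be near zero, zero or negative, and the plan has no rule for those cases

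*Combined protocol and SAP*

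**What the plan says.** Section 6.3.1.1 exposes K562 and Raji target cells to NK cells enriched from the patient's blood, at "3-fold serial dilutions of the effector cells, performed in triplicate". Lytic activity, in percent, is "sample 7AAD uptake - %minimum 7AAD uptake". The subtracted term has its own source: "Background (minimum) 7AAD uptake is calculated from targets incubated without effectors".

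The section then states that the NK functional response "is defined as percent increase of NK cell lytic activity at 1 day and 1 month post NK cell-enriched DLI". The reference value is the patient's own lysis before the infusion. The section gives no floor, offset, log scale or rule for a baseline at or below zero. It does not say which target line, which dilution or what summary over dilutions supplies the value, and it names no model or test for the percent increase.

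The functional NK lysis assay is part of secondary objective 2. For immune function, section 6.3 plans plots per patient and mean summaries: "The means of the measurements across patients will be calculated with their 95% confidence intervals". It adds a longitudinal model: "The generalized estimating equation method will be used to estimate the rates of change". No arm term or baseline covariate is mentioned. Section 6.31 adds medians at each time point and individual lines for the same assays.

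**The concern.** A ratio is a safe measure of response only when its denominator is clearly positive. Here the denominator is a difference of two measured percentages. When a patient's NK cells lyse few targets before the infusion, that difference is small and mostly noise, and it can fall to zero or below. The response is then extreme, undefined or of the wrong sign, although the post-infusion assay may be perfectly good.

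Activation of NK cells is the protocol's reason for adding DUK-CPG-001 (sections 2.8, 2.13 and 2.14), and this is the only NK-function response variable that the plan defines. If a handful of low baselines drive it, the summary may say more about those baselines than about the treatment. Leaving the target line and dilution open adds a choice that could be made after the data are seen.

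**Working it through.** **Inputs from the protocol.** Lytic activity L = S - M, where S is sample uptake and M is background uptake, both in percent (6.3.1.1). Response R = 100 x (L_post - L_pre) / L_pre (6.3.1.1). There are 25 patients per arm in each cohort (section 6.0), a number set by the primary two-stage designs. The documents give no baseline lysis distribution, assay error, pre/post correlation, effect size, alpha or power for this endpoint, so there is no stated figure to reproduce.

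**Step 1: can the denominator reach zero?** M comes from separate wells and has its own error. If true lysis is near zero, L is negative whenever M happens to read above S. Nothing in the definition prevents this.

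**Step 2: the same biological gain from different baselines.** With L_post - L_pre = +5 points:

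| L_pre | R = 100 x 5 / L_pre |
|---|---|
| 20 | +25% |
| 5 | +100% |
| 1 | +500% |
| 0.5 | +1000% |
| 0 | undefined |
| -1 | -500% |

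**Step 3: influence on an arm of 25.** Suppose 24 patients go from 20 to 25 (R = 25% each, sum 600) and the last patient also gains 5 points.
- Last baseline 0.5: mean R = (600 + 1000)/25 = 64%.
- Last baseline 1: mean R = (600 + 500)/25 = 44%.
- Last baseline -1: mean R = (600 - 500)/25 = 4%.

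Every patient gained the same 5 points. The median stays at 25% in all three cases, and the mean gain in percentage points stays at 5.

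**Step 4: which value enters the ratio.** With serial dilutions, lysis should approach background as effectors become fewer. The choice of dilution therefore moves L_pre towards zero or away from it, and the choice of target line can too. One blood sample can give quite different values of R, and the definition does not choose among them.

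**Step 5: illustrative power, every assay value assumed.** This compares a t test on R with ANCOVA on percent lysis (baseline as covariate), 25 per arm, two-sided 0.05.

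*Model A.* Bivariate normal, correlation 0.5, additive effect 0.7 SD, 3,000 trials; R is computed for positive baselines only, which is a rule of the simulation and not of the plan.

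| Baseline mean, SD | t test on R | ANCOVA |
|---|---|---|
| 20, 6 | 0.48 | 0.79 |
| 20, 10 | 0.27 | 0.80 |
| 10, 6 | 0.21 | 0.79 |

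Over correlations 0.3 to 0.7 the ranges are 0.15-0.70 and 0.71-0.92. A rank test on R reaches 0.54-0.58 at correlation 0.5. As a check, the ANCOVA variance factor is 1 - 0.5^2 = 0.75, so the effective effect is 0.7/sqrt(0.75) = 0.81 SD; a two-sample comparison at 0.8 SD with 25 per arm has power 0.81. In the last row, the normal probability below -10/6 gives about 5% of baselines at or below zero.

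*Model B.* True baselines always positive (lognormal), assay error SD 2 or 3 points, effect either 40% proportional or additive at 0.4 x the mean, 1,500 trials per setting. Ranges are over error and effect type.

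| Baseline mean (SD) | Share at or below 0 | t test on R | Rank test on R | ANCOVA |
|---|---|---|---|---|
| 5 (3) | 5-10% | 0.03-0.08 | 0.17-0.39 | 0.34-0.57 |
| 10 (6) | 0.7-2% | 0.16-0.45 | 0.47-0.84 | 0.62-0.84 |
| 20 (10) | 0-0.1% | 0.67-0.95 | 0.80-0.98 | 0.84-0.93 |
| 30-40 (12) | 0 | 0.90-0.99 | 0.90-0.99 | 0.90-0.97 |

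At mean 20, the t test on R ranges from no loss (0.95 against 0.93) to a loss of 0.16 (0.67 against 0.84 before rounding). At the same mean and SD, Model A shows a loss of 0.53. The models also differ in effect and correlation, so the size of the loss follows the assumptions, and the documents do not say which set is closer to the assay.

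**The case against.** The best defence is that this is one derived measure within a largely descriptive secondary objective. Sections 6.3 and 6.31 already plan means with confidence intervals, GEE rates of change, medians and individual plots for immune function, so lysis on its own scale will be reported whatever happens to the ratio. Medians resist the distortion in Step 3. True lysis cannot be negative, so a non-positive baseline arises only from noise, and replication in triplicate reduces noise. The documents refer assay details to an earlier study by the same group, which may show that baselines are comfortably high. All of this stands, and it limits the importance of the point. It does not repair the definition in 6.3.1.1, which still gives no answer at zero and a reversed one below it.

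Two stronger readings are tempting. A reader might infer that the plan throws away most of the power that baseline adjustment would give. The documents do not support that: they state no between-arm test and no power for this endpoint, and Step 5 shows that the loss can be absent. The t tests and Mann-Whitney tests in 6.31 stand in the microbiota paragraph; if the latter were read as covering NK response, the analysis would be rank-based, which loses less. A reader might also infer that patients with a non-positive baseline will be dropped. No such rule is written; their handling is simply unspecified.

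**Conclusion.** The definition is unstable as written. That conclusion needs only the two formulas in 6.3.1.1: an identical 5-point gain can read as +25%, +500%, undefined or -500%, and one patient in 25 can move an arm mean from 25% to 64% or to 4%. The missing choice of target line and dilution is a second gap in the same definition.

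How often this would bite is unknown, because the documents give no baseline distribution. Under the assumed models, loss of power for a mean-based comparison is large at low or variable baselines (means of 5-10 points) and absent or small at 30-40. At 20 it depends on the model. These figures illustrate the sensitivity and do not describe a planned test. The primary conclusions on progression-free survival and toxicity are unaffected. The point is a low-cost improvement to a secondary endpoint.

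**What to change.** Redefine the NK functional response as percent lysis, in percentage points, at one prespecified effector:target ratio for each of K562 and Raji, at 1 day and 1 month.

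Estimate the arm difference with a 95% confidence interval, adjusting for pre-DLI lysis and for disease type, the stratification factor. Use ANCOVA at each time point, or add baseline and arm terms to the planned GEE. Because the primary endpoints are analysed separately in Cohorts A and B, do this within each cohort or with cohort as a factor, and say which. Take the value before the first DLI as the covariate for the arm comparison, since the value before the second is measured after treatment has begun. Present the result as estimation for a secondary objective, without a claim of confirmatory testing.

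Report percent increase descriptively only, as a median, and state how non-positive baselines are handled. For example, count such patients, show their percent increase as not calculable, and keep them in the percentage-point analysis.

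No new samples or assays are needed, because the pre-DLI measurement is already scheduled. The cost is SAP wording and a small amount of extra analysis, including an arm estimate that the plan does not now specify.

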7.0 SAFETY MONITORING AND REPORTING

The PI is responsible for the identification and documentation of adverse events and serious adverse events, as defined below. At each study visit, the PI or designee must assess, through non-suggestive inquiries of the subject or evaluation of study assessments, whether an AE or SAE has occurred.

7.1 Adverse Events

An adverse event (AE) is any untoward medical occurrence in a subject receiving study drug and which does not necessarily have a causal relationship with this treatment. For this protocol, the definition of AE also includes worsening of any pre-existing medical condition. An AE can therefore be any unfavorable and unintended or worsening sign (including an abnormal laboratory finding), symptom, or disease temporally associated with the use of study drug, whether or not related to use of the study drug. Abnormal laboratory findings without clinical significance (based on the PI's judgment) should not be recorded as AEs. But laboratory value changes that require therapy or adjustment in prior therapy are considered adverse events.

From the time the subject is screened through the End of Study visit (as defined in Section 10.6), all AEs must be recorded in the subject medical record and adverse events case report form.

AEs will be assessed according to the CTCAE version 4.0. If CTCAE grading does not exist for an AE, the severity of the AE will be graded as mild (1), moderate (2), severe (3), life-threatening (4), or fatal (5).

Attribution of AEs will be indicated as follows:

- Definite: The AE is clearly related to the study drug
- Probably: The AE is likely related to the study drug
- Possible: The AE may be related to the study drug
- Unlikely: The AE is doubtfully related to the study drug
- Unrelated: The AE is clearly NOT related to the study drug

7.2 Serious Adverse Events

An AE is considered “serious” if in the opinion of the investigator it is one of the following outcomes:

- Fatal
- Life-threatening
- Constitutes a congenital anomaly or birth defect
- A medically significant condition (defined as an event that compromises subject safety or may require medical or surgical intervention to prevent one of the three outcomes above).
- Requires inpatient hospitalization or prolongation of existing hospitalization
- Results in persistent or significant incapacity or substantial disruption to conduct normal life functions.

7.2.1 Reporting of SAEs

Any reactions that is reportable (serious, unexpected and related/possibly related to the study) must be reported using the FDA #3500 MedWatch form and the Duke University Health System (DUHS) Institutional Review Board (IRB) Office SAE form. All other side effects and toxicities will be recorded in the patient’s research chart or documented on the computer record for the patient.

7.3 Special Warnings and Precautions

Specific plan in the event of microbial contamination of infused cellular product:

Product sterility testing will include a STAT gram stain which will have to be negative prior to release for infusion. A 14 day culture will be performed by our microbiology laboratory as per FDA requirements. In addition, per the SOP of sterility testing, cultures will be maintained for 5 days in our stem cell laboratory though typically the product is infused fresh the day of collection or the following day. In the event that a culture becomes positive, the lab notifies the treating physician immediately who in turn notifies the patient and the treating staff. Patients will be evaluated within the same day of notification of a positive culture by the treating team for any infection related incidents and treated appropriately. The evaluation will include a minimum of physical examination, vital signs and blood culture.

In the event of this occurrence, this will be considered an SAE and reported in an expedited manner as above for other serious adverse events if there is a change in the health status of the patient or requiring initiation of antimicrobials. Microbial contamination will otherwise be reported to the IND as an adverse event amendment submission within 7 days of occurrence.

Investigation plan in case of cellular microbial contamination:

In the event that a product has a positive culture, all reasonable efforts will be undertaken to detect the possible source. For potential donor source, donor notification and return to clinic or primary care physician for examination if there are any signs or symptoms of infection will be recommended. Examination of the chain of custody log to ensure proper transit of the product and review of the exact procedure with the laboratory technician who performed the cell selection to investigate any potential difficulties that arose (tubing malfunction, bag leakage, etc). If two such events are noted in the this

study without a correctable cause being found after investigation, the trial will be closed to accrual until the Duke cryo lab staff assigned to this study has been inserviced by a company representative from Miltenyi and the above issues are reviewed. Staff assigned and undergoing this additional education will be logged with a copy in the regulatory files for documentation. Upon reopening accrual, increased point of care testing for sterility will be added to our SOP at the following points:

- In the clinic after collection and prior to transmission to cryo-lab
- In the cryo-lab just prior to putting the product on the Miltenyi device
- in the cryo lab after completion of manipulation on the device and before transmission to the clinical lab for infusion
- In the clinic just prior to infusion into the patient

7.4 Safety Oversight Committee (SOC)

The Duke Cancer Institute SOC is responsible for annual data and safety monitoring of DUHS sponsor-investigator phase I and II, therapeutic interventional studies that do not have an independent Data Safety Monitoring Board (DSMB). The primary focus of the SOC is review of safety data, toxicities and new information that may affect subject safety or efficacy. Annual safety reviews includes but may not be limited to review of safety data, enrollment status, stopping rules if applicable, accrual, toxicities, reference literature, and interim analyses as provided by the sponsor-investigator. The SOC in concert with the DCI Monitoring Team (see Section 12.1 for Monitoring Team description) oversees the conduct of DUHS cancer-related, sponsor-investigator greater-than-minimal-risk intervention studies that do not have an external monitoring plan, ensuring subject safety and that the protocol is conducted, recorded and reported in accordance with the protocol, standing operating procedures (SOPs), Good Clinical Practice (GCP), and applicable regulatory requirements.

8 QUALITY CONTROL AND QUALITY ASSURANCE

8.1 Monitoring

The Duke Cancer Institute (DCI) Monitoring Team will conduct monitoring visits to ensure subject safety and to ensure that the protocol is conducted, recorded, and reported in accordance with the protocol, standard operating procedures, good clinical practice, and applicable regulatory requirements. As specified in the DCI Data and Safety Monitoring Plan, the DCI Monitoring Team will conduct routine monitoring after the third subject is enrolled, followed by annual monitoring of 1 – 3 subjects until the study is closed to enrollment and subjects are no longer receiving study interventions that are more than minimal risk.

Additional monitoring may be prompted by findings from monitoring visits, unexpected frequency of serious and/or unexpected toxicities, or other concerns and may be initiated upon request of DUHS and DCI leadership, the DCI Cancer Protocol Committee, the Safety Oversight Committee (SOC), the sponsor, the Principal Investigator, or the IRB. All study documents must be made available upon request to the DCI Monitoring Team and other authorized regulatory authorities, including but not limited to the National Institute of Health, National Cancer Institute, and the FDA. Every reasonable effort will be made to maintain confidentiality during study monitoring.

8.2 Audits

The Duke University Office of Audit, Risk and Compliance - Human Subjects Research Compliance (HSRC) office may conduct confidential audits to evaluate compliance with the protocol and the principles of GCP. The PI agrees to allow the HSRC auditor(s) direct access to all relevant

documents and to allocate his/her time and the time of the study team to the HSRC auditor(s) in order to discuss findings and any relevant issues.

HSRC audits are designed to protect the rights and well-being of human research subjects. HSRC audits may be routine or directed (for cause). Routine audits are selected based upon risk metrics generally geared towards high subject enrollment, studies with limited oversight or monitoring, Investigator initiated Investigational Drugs or Devices, federally-funded studies, high degree of risk (based upon adverse events, type of study, or vulnerable populations), Phase I studies, or studies that involve Medicare populations. Directed audits occur at the directive of the IRB or an authorized Institutional Official.

HSRC audits examine research studies/clinical trials methodology, processes and systems to assess whether the research is conducted according to the protocol approved by the DUHS IRB. The primary purpose of the audit/review is to verify that the standards for safety of human subjects in clinical trials and the quality of data produced by the clinical trial research are met. The audit/review will serve as a quality assurance measure, internal to the institution. Additional goals of such audits are to detect both random and systemic errors occurring during the conduct of clinical research and to emphasize “best practices” in the research/clinical trials environment.

8.3 Data Management and Processing

8.3.1 Case Report Forms (CRFs)

An electronic CRF maintained in a Microsoft Office Access database will be the primary data collection document for the study. The CRFs will be updated in a timely manner following acquisition of new source data. Only approved study staff (data coordinators), are permitted to make entries, changes, or corrections in the CRF.

An audit trail will be maintained automatically by the electronic CRF management. Designated personnel will complete user training, as required or appropriate per regulations.

8.3.2 Data Management Procedures and Data Verification

Designated personnel using the electronic CRF will have access based on their specific roles in the protocol. Regulatory and nursing coordinators will have read-only access. Data Coordinators will have edit access.

Completeness of entered data will be checked automatically by the eCRF system, and users will be alerted to the presence of data inconsistencies. Additionally, the data manager and/or data coordinator back-up will cross-reference the data to verify accuracy. Missing or implausible data will be highlighted for the PI requiring appropriate responses (i.e. confirmation of data, correction of data, completion or confirmation that data is not available, etc.).

The database will be reviewed and discussed prior to database closure, and will be closed only after resolution of all remaining queries. An audit trail will be kept of all subsequent changes to the data.

8.3.3 Study Closure

Following completion of the studies, the PI will be responsible for ensuring the following activities:

- Data clarification and/or resolution

- Accounting, reconciliation, and destruction/return of used and unused study drugs
- Review of site study records for completeness
- Shipment of all remaining laboratory samples to the designated laboratories

